5.8 Premature Termination or Suspension of Study

This study may be temporarily suspended or prematurely terminated if there is sufficient reasonable cause. Written notification, documenting the reason for study suspension or termination, will be provided by the suspending or terminating party to investigator, funding agency, the IDE sponsor and regulatory authorities. If the study is prematurely terminated or suspended, the PI will promptly inform the IRB and will provide the reason(s) for the termination or suspension.

Circumstances that may warrant termination or suspension include, but are not limited to:

- Determination of unexpected, significant, or unacceptable risk to participants
- Insufficient compliance to protocol requirements
- Data that are not sufficiently complete and/or evaluable

Study may resume once concerns about safety, protocol compliance, data quality are addressed and satisfy the sponsor, IRB and/or FDA.

6 Study Agent (Study device) and/or Procedural Intervention

6.1 Study Device Description

Embozene™ Microspheres are spherical, tightly calibrated, biocompatible, nonresorbable, hydrogel microspheres coated with an inorganic perfluorinated polymer (Polyzene™-F). The microspheres intended to occlude vasculature for the purpose of blocking blood flow to a target tissue. They are available in prefilled syringes in a range of sizes suitable for embolic therapy. The microspheres are compressible to enable smooth delivery through the indicated delivery catheter and color-coded by size to allow for easy identification. 250 µm microsphere will be used and are supplied in prefilled yellow syringes.

Embozene Microspheres are intended for embolization of arteriovenous malformations and hypervascular tumors, including uterine fibroids and hepatoma, and for embolization of prostatic

CONFIDENTIAL

arteries for symptomatic benign prostatic hyperplasia. This device is not intended for neurovascular use. The device is FDA approved for above indications (FDA approved for treatment of BPH; FDA approval 510(K) # K180102; 510(k) premarket notification of intent to market the device FDA 510(k) # K141209)

There are no known chemical interactions between Embosphere Microspheres and pharmaceuticals.

IDE for the purpose of this study was obtained.

6.1.1 Acquisition

Embosphere™ Microspheres will be supplied by the manufacturer.

6.1.2 Formulation, Appearance, Packaging, and Labeling

Embosphere Microspheres are supplied in a 20 ml syringe prefilled with 2 ml of product suspended in a non-pyrogenic, sterile transport solution of physiological saline. The total volume of Embosphere Microspheres including transport solution is approximately 7 ml. Prefilled syringes of Embosphere Microspheres are packaged in a sterile, sealed tray with a peel-away lid. The label indicates the specific size of the microspheres contained in the syringe. 250 µm microsphere will be used and are supplied in prefilled yellow syringes.

6.1.3 Product Storage and Stability

As per manufacturer's instructions specified in the DFU, the device should be stored in a cool, dry, dark place. Product must be used prior to expiration date on label. The investigational device will be stored in a secure locked cabinet in the interventional radiology storage area (Tisch hospital, 2nd floor) and only the PI and research coordinator will have access to the lock.

6.1.4 Preparation

Embosphere Microspheres are supplied in a 20 ml syringe prefilled with 2 ml of product suspended in a non-pyrogenic, sterile transport solution of physiological saline. The total volume of Embosphere Microspheres including transport solution is approximately 7 ml.

Prior to embolization, the transport solution will be eliminated from the syringe. An embolic mixture will be prepared by adding 9 cc saline + 9 cc iodinated contrast added to the 2 cc of product (Embosphere Microspheres) for a total of 20 cc embolic mixture.

6.1.5 Dosing and Administration

The embolic mixture will be injected in small increments until blood flow stagnates in the target artery (1 cc embolic mixture injected over 2 minutes, followed by 1 cc saline delivered slowly, then 3 cc saline flush).

6.1.6 Route of Administration

The embolic mixture will be injected in small increments in the target geniculate artery(ies) after selective catheterization of the target vessel(s) using a microcatheter to reach distal arteries while avoiding branches that do not feed abnormal vessels.

6.1.7 Duration of Therapy

Treatment will be completed during one interventional session (visit 3, day 0)

CONFIDENTIAL

6.1.8 Device Specific Considerations

Embozene microspheres are available in prefilled syringes in a range of sizes suitable for embolic therapy. 250 µm microspheres syringes will be used for this study and are supplied in prefilled yellow syringes.

6.2 Study Procedural Intervention(s) Description

On the day of the procedure (visit 3, day 0), the subjects will be given the choice of receiving intravenous anxiolytic and analgesic medication (moderate sedation) during procedure or proceeding with local anesthetic only. Arterial access site will be prepped and draped using sterile technique. Femoral artery access will be obtained with a micropuncture needle set and a vascular sheath or a guiding catheter will be placed in the femoral artery to maintain vascular access. Ultrasound-guided access may be used. A guiding catheter will be introduced and lower extremity digital subtraction angiography will be performed to depict the descending genicular artery, superior and inferior lateral genicular arteries, superior and inferior medial genicular arteries, and the median genicular artery in all patients. Angiography will be performed to identify abnormal knee neovasculature arising from one or more of geniculate arterial branches.

After localizing the abnormal neovessels (abnormal vessels appear as tumor blush–type enhancement in the arterial phase, often accompanied by early venous drainage /hypervascular synovial tissue in the region of the target knee joint), a microcatheter will be inserted coaxially through the guiding catheter and selectively placed in the targeted artery(ies). If there is uncertainty about the angiographic findings, pre-embolization simulation can be performed with contrasted cone beam CT on the procedure table. This will allow the operators to know exactly what tissues will be receiving the microspheres. The abnormal vessels will be embolized with 250 µm Embozene™ Microspheres solution under direct fluoroscopic visualization to prevent reflux and non-target embolization. Multiple geniculate arteries may be embolized until neovascularity is no longer seen.

The embolic mixture will be prepared by adding 9 cc of saline + 9 cc of contrast to the 2 cc Embozenespheres for a total of 20 cc embolic mixture. Injection of the embolic mixture will continue in small increments until an end point of at least ‘pruning’ of the hypervascular synovium’ (slowed antegrade flow of contrast).in the target artery(ies) (1 cc embolic mixture injected over 2 minutes, followed by 1 cc saline delivered slowly, then 3 cc saline flush). In some cases, more selective catheterization will be performed by using the microcatheter to reach distal arteries while avoiding branches that do not feed abnormal vessels. After embolization, a repeat lower extremity angiogram and contrasted cone beam CT (if needed) will then be performed to evaluate for success of embolization and to exclude complication. The catheter(s) and sheath will be removed, and hemostasis of the arterial access will be achieved by an FDA-approved arterial closure device or manual compression and bed rest for 2-6 h after the femoral artery sheath removal. All participants will be monitored for 2-6 hours post procedure and any adverse events will be documented and managed. If hemostasis obtained by a vascular closure device, it is anticipated that most participants will be discharged home 2 hours post procedure. If hemostasis obtained by manual compression, it is anticipated that most participants will be discharged home 6 hours post procedure.

Disposable syringes which spherical particulate will be discarded as medical waste and packaging will be kept in a secure location until the study is completed. Packages will be disposed of upon completion of the study.

6.2.1 Administration of Procedural Intervention

Procedure will be performed by one of two interventional radiologists with fellowship training in Vascular and Interventional Radiology. The interventional procedure will be performed during one session (day 0) with an approximate duration of the procedure estimated between 1-3 hours. Additional 2-6 hours will be needed after hemostasis of the access femoral artery is achieved for monitoring / observation. In general, the subject will be discharged home the same day (<23 hours) unless a complication arises that requires inpatient admission for management of the complication.

CONFIDENTIAL

7 Study Procedures and Schedule

7.1 Study Procedures/Evaluations

7.1.1 Study Specific Procedures

- Medical history
 - Complete medical history will be obtained from medical records if available and/or by interview during clinic visits.
- History of previous and concomitant treatment
 - Knee injections and frequency over the 12 months
 - Medication history over the last month will be obtained during pre and post intervention study visits. Medication history will focus on medications currently taken for the treatment of knee OA; including prescription and over-the-counter medications for pain.
 - Physical therapy and frequency over the 12 months
 - Weight loss / gain
- Focused physical examination:
 - Vital signs (temperature, blood pressure, heart rate, oxygen saturation, height, weight, BMI)
 - Focused knee examination.
 - Lower extremity pulses
- Imaging assessment with knee MRI
 - Baseline and follow-up (at 3 months) knee MRI will be performed.
 - Knee MRI protocol will include: Axial t2 FS, Sagittal PD, Sagittal T2 FS, Coronal PD FS, Coronal PD FS, non-contrast axial and sagittal T1 FS.
 - Imaging variables collected for this study is found in the attached eCRFs
- A discussion of the results of any study specific procedures (e.g., radiographic or other imaging or laboratory evaluations) will be provided to participant after the completion of the study unless these information represent a significant health-related issue.
- Laboratory tests:
 - Baseline and follow-up (at 1-, 3-, and 12-, 18-48 months) laboratory tests will be obtained
- Administration of questionnaires or other instruments for patient-reported outcomes:
 - Electronic VAS
 - KOOS questionnaire
 - Self-reported quality of life EQ-5D-5L questionnaire

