3.2 Secondary Objectives

The secondary objectives of the study are to determine whether genicular artery embolization is effective in improving

1. Knee pain using an electronic VAS at 1-, 3-, and 12-months (and final 18-48 months visit) post intervention
2. Knee pain using WOMAN pain score at 1- and 12-months (and final 18-48 months visit) post intervention
3. Knee stiffness using the WOMAC knee stiffness score at 1-, 3-, and 12- months (and final 18-48 months visit) post intervention
4. Physical function using the WOMAC function score at 1-, 3-, and 12- months (and final 18-48 months visit) post intervention
5. Self-reported quality of life using EQ-5D-5L scale at 1-, 3-, and 12- months (and final 18-48 months visit) post intervention [28]
6. Synovitis on MRI at 3 months post intervention

Other secondary objectives are to assess

1. Feasibility / technical success defined as successful selective catheterization of target vessel(s) and embolization from at least one feeding artery of the knee joint (with the embolization endpoint defined as suppression or reduction in the filling of (and therefore blood flow in) abnormal vessels visible on angiography).
2. Reduction in frequency of pain medication usage over 30-day period assessed at baseline and at 1, 3, and 12 months follow-up visits post intervention (acetaminophen, over the counter NSAIDs, prescription NSAIDs, opioids)
3. Reduction in frequency of knee injection therapy over 12-month period (assessed at baseline and at 12-month follow-up visit post intervention)
4. Reduction in frequency of need for physical therapy over 12-month period (assessed at baseline and at 12-month follow-up visit post intervention)
5. Safety evaluated by cumulative rates of adverse events (AE), as well as type and severity of each adverse event.

4 Study Design and Endpoints

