4.2.2 Secondary Study Endpoints Analysis

Secondary efficacy endpoints are:

- 1- WOMAC pain score at 1- and 12- months (and final 18-48 months visit) post intervention
- 2- Pain electronic VAS at 1-, 3-, and 12- months (and final 18-48 months visit) post intervention
- 3- Knee stiffness WOMAC score at 1-,3-, and 12- months (and final 18-48 months visit) post intervention
- 4- Physical function WOMAC score at 1-, 3-, and 12- months (and final 18-48 months visit) post intervention
- 5- Total WOMAC score at 1-,3-, and 12- months post intervention
- 6- Self-reported quality of life using EQ-5D-5L scale at 1-, 3-, and 12- months (and final 18-48 months visit) post intervention.
- 7- MRI findings at 3- months post intervention
- 8- Pain medication usage at 1-, 3-, and 12- months (and final 18-48 months visit) post intervention
- 9- Injection therapy requirements (hyaluronic acid or steroid) at 12- months (and final 18-48 months visit) post intervention
- 10- Physical therapy requirements at 12- months (and final 18-48 months visit) post intervention
- 11- Feasibility / technical success
- 12- Laboratory findings at 1-, 3-, and 6- months (and final 18-48 months visit) post intervention

Secondary safety endpoints are:

- 13- Number/rate, severity, and description of complications, adverse events, or poor outcomes that are secondary to the procedure, which will be summarized using counts and simple statistics (i.e., mean number of patients with complications.)

CONFIDENTIAL

5 Study Enrollment and Withdrawal

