5.1 Inclusion Criteria

In order to be eligible to participate in this study, an individual must meet all the following criteria:

1. 30-80 years of age of any gender and;
2. Kellgren-Lawrence Grade 2, 3, or 4 (in select subjects who have no bony deformity)* knee OA on most recent knee radiograph obtained within 6 months of screening visit and;
3. Knee pain resistant to conservative treatment for at least 3 months* (anti-inflammatory drugs, acetaminophen, physical therapy, muscle strengthening, or intra-articular injection of hyaluronic acid and/or steroids); and
4. Moderate to severe knee pain: pain VAS ≥ 40 mm with 0 representing 'no pain' and 100 'the worst pain imaginable'. If both knees meet inclusion criteria, the one with a higher VAS score will be chosen for the study (i.e., target knee).
5. Willing, able, and mentally competent to provide informed consent and complete study questionnaires in English. The Study questionnaire is validated in English.

A recent study by Padio S et al included subjects with KL grade 4 and published results showed, similar to other studies, clinical reduction in pain score with no added risks. The scientific rationale for adding these subjects with KL grade 4 (severe knee OA with no bone deformity) is based on recent literature data (Citation: JB JS Open Access. 2021 Oct-Dec; 6(4): e21.00085.)

*3 months was chosen because this time interval is thought adequate for knee pain to be considered refractory to conservative care.

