5.2 Exclusion Criteria

An individual who meets any of the following criteria will be excluded from participation in this study:

1. Active systemic or local knee infection or;
2. Active malignancy or;
3. Life expectancy less than 12 months or;
4. Prior ipsilateral knee surgery (within 3 years of baseline visit), arthroscopic surgery (within 6 months of baseline), total or partial knee replacement regardless of timing or;
5. Ipsilateral knee intra-articular injection in the last 3 months or;
6. Rheumatoid arthritis, spondyloarthropathies, crystal disease, gout, pseudogout, or lupus;
7. Pregnant during the study period or;
8. Renal dysfunction as defined by serum creatinine > 1.6 dl/mg or eGFR < 60 on blood tests obtained within 30 days of procedure or;
9. Body weight greater than 200 Kg or;
10. Uncorrectable coagulopathy (platelet count $< 50,000$, international normalized ratio > 1.5 within 30 days of procedure; or
11. Known history of contrast allergy resulting in anaphylaxis or;
12. Known significant arterial atherosclerosis that would limit selective angiography and/or lower extremity symptoms thought to be secondary to arterial vascular disease (eg claudication, ischemic rest pain)
13. Post-traumatic knee (if trauma occurred within 12 months of baseline or was associated with fractures)
14. known avascular necrosis in the target knee
15. Contraindications to MRI such as such as claustrophobia, metallic fragment/implants, pacemaker.

CONFIDENTIAL

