10.4.3 Analysis of the Secondary Endpoint(s)

Analysis of secondary endpoints include: (1) changes in the mean WOMAC and VAS pain scores, the mean WOMAC knee stiffness and physical function scores and the total WOMAC knee physical function score; (2) the technical success rate (defined as the proportion of patients for whom the procedure was successfully completed); (3) the adverse event rate (defined as the proportion of patients showing each type of adverse event or any adverse event); (4) reduction in the usage of pain medication, the frequency of infection therapy, the need for physical therapy; and (5) the proportion of patients showing synovial thickening, joint effusion, meniscus tear, synovial enhancement, osteophytes. A point estimate and 95% confidence interval will be provided for each secondary outcome at each time and for the change in each outcome from baseline to each post-treatment follow-up visit. Changes in the outcomes from baseline to follow-up will be tested using the paired-sample Wilcoxon signed rank test for the WOMAC and VAS scores and the McNemar test for the other measures which will be assessed as binary outcomes (e.g., whether or not the patient reported usage of pain medication on a daily basis).

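### Physical therapy is both a qualifying failed treatment and a before-after outcome, so the planned McNemar test can show a drop in its use without any effect of embolization

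*Combined protocol and SAP*

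**What the plan says.** Section 5.1, criterion 3, admits patients with "Knee pain resistant to conservative treatment for at least 3 months". The qualifying treatments are anti-inflammatory drugs, acetaminophen and "physical therapy, muscle strengthening, or intra-articular injection of hyaluronic acid and/or steroids". The three months are a minimum duration. Nothing says how recently a treatment must have been given, and the options are alternatives.

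Section 3.2, in its second list, sets the objective "Reduction in frequency of need for physical therapy over 12-month period (assessed at baseline and at 12-month follow-up visit post intervention". Section 4.2.2, item 10, lists the endpoint as "Physical therapy requirements at 12- months (and final 18-48 months visit) post intervention". Section 7.1.1 collects the data as "Physical therapy and frequency over the 12 months". I read these together as the year before baseline set against the year after the procedure.

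Section 10.4.3, item (4), includes the need for physical therapy among the secondary analyses. It assigns the Wilcoxon signed rank test to the WOMAC and VAS scores and "the McNemar test for the other measures which will be assessed as binary outcomes". Physical therapy therefore falls under McNemar, although the cut-point that makes it binary is not given. The study has one arm and no sham or placebo (Sections 4.1 and 10.2), and Section 10.1 says that no formal SAP will be produced.

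**The concern.** McNemar's null hypothesis is that use is equally common before and after. That is a fair reference only if, without a treatment effect, the two years would be alike. Here the entry rule bears on one year and not the other. A patient who qualified because physical therapy failed within the look-back has a baseline value of yes by selection. No rule requires therapy in the follow-up year, and a therapy already judged ineffective may be dropped whatever embolization does. Since the protocol gives no criterion for when therapy is needed, giving it up because it failed would count as reduced need.

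This is more specific than regression to the mean in an uncontrolled study: the eligibility criterion names the outcome variable. I found no control group, no rule separating the qualifying course from the baseline count, and no caveat for this endpoint. At stake is the reading of one secondary result: a significant drop could be taken as a benefit of embolization when selection alone can produce it.

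**Working it through.** **The plan's own figures.** The documents give no rate, power or sample size for physical therapy. The only sizing is for the primary endpoint, and it reproduces: with X binomial on 23 patients, P(X ≥ 16) is 0.0466 at a true proportion of 0.5 (stated 0.047) and 0.8037 at 0.75 (stated 80.4%). With 20% attrition, 23/0.8 = 28.75, so 29, and 40/0.8 = 50. None of this bears on physical therapy.

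**Inputs from the documents.** 40 evaluable patients (Section 5.6); paired before-after comparison over two 12-month periods (Section 3.2); McNemar test (Section 10.4.3); one arm.

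**Assumed inputs.** Two-sided 5% level and the exact form of the test, neither stated for this endpoint; ordinary yearly use u of 20% to 50%; share s of patients enrolled because of failed physical therapy inside the look-back, from 0 to 50%; independence of the two years within a patient; no treatment effect.

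**Model.** Patients in share s have baseline value yes; the others have it with probability u. Everyone has follow-up value yes with probability u.

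- Baseline rate: b = s + (1 − s)u
- Follow-up rate: u
- Yes then no: p10 = b(1 − u)
- No then yes: p01 = (1 − b)u

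The chance of a significant drop is the sum, over all discordant counts among 40 patients, of outcomes with more yes-then-no than no-then-yes pairs and an exact two-sided p-value of at most 0.05.

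**Worked case.** For u = 0.30 and s = 0.20, b = 0.20 + 0.80 × 0.30 = 0.44, p10 = 0.44 × 0.70 = 0.308 and p01 = 0.56 × 0.30 = 0.168. The chance of a significant drop is 18.4%.

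**Results (chance of a significant drop, no treatment effect).**

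| Ordinary use u | s = 0 | s = 10% | s = 20% | s = 30% | s = 50% |
|---|---|---|---|---|---|
| 20% | 1.3% | 8.3% | 27.0% | 54.6% | 93.9% |
| 30% | 1.5% | 6.4% | 18.4% | 38.8% | 83.5% |
| 40% | 1.5% | 5.0% | 13.1% | 27.7% | 69.6% |
| 50% | 1.5% | 4.1% | 9.8% | 20.0% | 54.8% |

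The nominal limit in this direction is 2.5%; the exact test is conservative, hence about 1.5% at s = 0.

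**Sensitivity.** Independence does not create the result. For baseline 50% against follow-up 30%, the chance is 35% with independent years, 43% with within-patient correlation 0.2 and 54% with 0.4. The asymptotic McNemar test gives higher values: 49% instead of 39% at u = 30% and s = 30%. A small excess does little: 35% against 30%, or 45% against 40%, gives about 4%.

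**The case against.** **Recency and direction.** A reader might infer that patients have only just failed physical therapy, that the baseline year is therefore loaded, and that the bias must always favour embolization. The documents do not support this. Criterion 3 sets a minimum duration and no recency limit. A patient whose physical therapy failed more than a year before baseline, and who has since given it up, would have low use in the look-back year, which works the other way. This stands: the loading depends on how many qualifying courses fall in the look-back.

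**Other routes to entry.** A patient can qualify on drugs alone. Exclusion criterion 5, "Ipsilateral knee intra-articular injection in the last 3 months", might be read as pushing recent treatment towards physical therapy, but it does not show that therapy fills the gap, and older injections still qualify. This also stands.

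**Size.** The large probabilities come from chosen inputs. If entry selects habitual users, their follow-up use would be high too and the gap would shrink. This is fair: the table shows what is possible and does not estimate what will happen.

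**A minor outcome in an openly uncontrolled pilot.** Section 3.2 states an objective and makes no claim of benefit, and success is judged on the WOMAC responder rate. This limits the weight of the point. It does not remove it, because a general remark that the study is uncontrolled would not tell readers that patients were selected on the very variable being tested.

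**Pain medication.** It is tempting to extend the argument, since drugs also qualify. That outcome uses a different, 30-day window (Section 3.2) and has not been examined here, so no conclusion is drawn.

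**Conclusion.** The point holds as a possibility built into the design: a significant fall in physical therapy use would not by itself be evidence of benefit. The chance of such a finding with no treatment effect ranges from about 1.5% when no qualifying therapy falls in the look-back, through 4-8% at a share of 10% and 10-27% at 20%, to 55-94% at 50%. These figures rest on 40 patients, an exact two-sided 5% test, ordinary use of 20-50%, follow-up use at the ordinary rate and independent years. The documents give neither the share nor the rates, so the actual size is unknown. A test on session frequency would carry the same selection. Only this secondary outcome is affected; the primary conclusion does not depend on it.

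**What to change.** - **Section 10.4.3, item (4).** Take physical therapy out of the McNemar-tested outcomes. Report, for each period, the proportion with any physical therapy and the session frequency, each with a 95% confidence interval, plus the baseline-by-follow-up two-by-two table. The section already calls for point estimates and intervals, so this mainly removes the test.
- **Classification.** From the previous-treatment history already collected at baseline (Schedule of Activities; Section 7.1.1), classify whether physical therapy in the look-back was a qualifying failed treatment. Show the table separately for patients in whom it was and was not. A new item at Visit 2 could not be prospective for patients already past 12 months, so this has to come from existing source documents.
- **Section 3.2.** Name the objective as a change in physical therapy instead of a reduction. Add one sentence saying that the before-after difference is not evidence of benefit, because entry selects on prior treatment.

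Cost: one fewer secondary significance test and some abstraction from existing records. No visit, procedure or eligibility rule changes.
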